## **7.6 Considerations for Phase 2 Expansion**

During Phase 2 expansion, if circumstances prevent a patient from completing on-site visits (e.g., precautions needed to mitigate risk to the patient during a pandemic, natural disaster, or social or political unrest), then the following procedures may be conducted off-site, with Sponsor approval in place before implementation of any off-site study procedures. This option applies only to patients who have completed at least 2 cycles of dosing and have completed study procedures on-site through Cycle 2 Day 28.

- Informed consent, as permitted by site IRB/EC, SOPs, and local regulatory authorities
- ECOG performance status test
- Laboratory assessments: hematology, chemistry, coagulation, urinalysis, and pregnancy testing (for FOCP)
- 12-lead ECG (single)
- Echocardiogram/MUGA scan
- Disease assessment by CT scan and MRI

- THE-630 administration
- THE-630 compliance
- Adverse events assessment
- Recording of concomitant medications

Off-site methods include but are not limited to the procedure(s) occurring at a facility closer to the patient's home and/or procedures conducted through remote methods (e.g., telemedicine). Sites must clearly document the details of all procedures and/or visits that are performed off-site.

## **8. ADVERSE EVENT DATA COLLECTION AND REPORTING**

### **8.1 Reference Safety Information**

The reference for safety information for this study is the IB which the Sponsor has provided under separate cover to all Investigators.

### **8.2 Definition of Adverse Events, Period of Observation, Recording of Adverse Events**

An Adverse Event (AE) is any untoward medical occurrence in a clinical investigation patient administered a pharmaceutical product and that does not necessarily have a causal relationship with this treatment. An AE can therefore be any unfavorable and unintended sign (including an abnormal laboratory finding), symptom, or disease temporally associated with the use of a medicinal (investigational) product, whether or not related to the medicinal (investigational) product ([ICH E2A, 1995](#)). All AEs should be captured on the AE eCRF.

All AEs are collected from the time of informed consent through at least 30 days after the last dose of study drug. Beyond 30 days after the last dose, ongoing AEs for which relationship to THE-630 cannot be ruled out, and all ongoing serious adverse events (SAEs) should be followed at least every 4 weeks until they resolve to baseline (or to NCI CTCAE v5.0 grade  $\leq 1$ ), stabilize, or are considered to be chronic/irreversible. In addition, SAEs observed by the investigator or reported by the patient that occur after 30 days after the last dose of study drug through the end of the survival follow-up period should be reported if there is a reasonable possibility that the event may have been caused by THE-630, even if the investigator becomes aware of such events after the end of the survival follow-up period.

Once a patient is deemed a screen failure, AE collection is no longer required.

All AEs are to be recorded on the appropriate AE pages in the eCRF and in source documents. Where possible, a diagnosis, rather than a list of symptoms, should be recorded. If a diagnosis has not been made, then each symptom should be listed individually. In addition to untoward AEs, unexpected benefits outside the study drug indication should also be captured on the AE eCRF.

#### **8.2.1 Severity Categorization**

AE severity should be graded per the NCI CTCAE v5.0 definitions listed in [Appendix 3](#).

The severity of AEs must be recorded over the course of the event, including the start and stop dates. An event that changes with worsening severity should be captured as a new event. Worsening of pre-treatment events, after initiation of study drug, must be recorded as new AEs (for example, if a patient experiences mild intermittent dyspepsia prior to dosing of study drug, but the dyspepsia becomes severe and more frequent after first dose of study drug has been administered, a new AE of severe dyspepsia [with the appropriate date of onset] is recorded on the appropriate eCRF).

If the AE is not defined in the CTCAE, the Investigator will determine the severity of the AE based on the following definitions:

- *Mild (grade 1)*: The AE is noticeable to the patient but does not interfere with routine activity
- *Moderate (grade 2)*: The AE interferes with routine activity but responds to symptomatic therapy or rest
- *Severe (grade 3)*: The AE significantly limits the patient's ability to perform routine activities despite symptomatic therapy
- *Life-Threatening (grade 4)*: The patient is at immediate risk of death
- *Death (grade 5)*: The patient dies as a direct result of the complication or condition induced by the AE

### **8.2.2 Relationship Categorization**

An Investigator must make the assessment of causal relationship to study drug for each AE. The Investigator should decide whether, in his or her medical judgment, there is a reasonable possibility that the event may have been caused by the study drug. If relationship to THE-630 can be clearly and incontrovertibly ruled out (e.g. due to the underlying disease or an extraneous cause), then the AE should be classified as "not related." Otherwise, without clear relationship to another cause, a possible cause-and-effect relationship between the study drug and the occurrence of the AE should be suspected and the AE should be considered "related." The causality assessment must be documented in the source document.

In addition, if the Investigator determines that an SAE is associated with study procedures, the Investigator must record this causal relationship in the source documents and on the SAE form and report such an assessment in accordance with the SAE reporting requirements.

The Investigator may change opinion of causality in light of follow-up information.

### **8.2.3 Outcome Categorization**

The outcome of AEs must be recorded during the study on the eCRF. Outcomes are as follows:

- Fatal
- Not Recovered/Not Resolved
- Recovered/Resolved

- Recovered/Resolved with Sequelae
- Recovering/Resolving
- Unknown

#### **8.2.4 Symptoms of the Disease Under Study**

Symptoms of the disease under study should not be classed as AEs as long as they are within the normal day-to-day fluctuation or expected progression of the disease. However, unexpected and significant worsening of the symptoms should be recorded as an AE.

Death due to disease progression in the absence of signs and symptoms should be reported as the primary tumor type (e.g., metastatic GIST).

**Note:** The term “disease progression” should not be used to describe the adverse event.

#### **8.2.5 Clinical Laboratory Evaluations**

A change in a clinical laboratory value can represent an AE if the change is clinically relevant or if, during treatment with the study drug, a shift of a parameter is observed from a normal value to an abnormal value, or a further worsening of an already abnormal value. When evaluating such changes, the extent of deviation from the reference range, the duration until return to the reference range, either while continuing treatment or after the end of treatment with the study drug, and the range of variation of the respective parameter within its reference range, must be taken into consideration.

If, at the end of the treatment phase, there are abnormal clinical laboratory values which were not present at baseline, further clinical or laboratory investigations should be performed until the values return to within the reference range or until a plausible explanation (e.g., concomitant disease) is found for the abnormal clinical laboratory values.

The Investigator should decide, based on the above criteria and the clinical condition of a patient, whether a change in a clinical laboratory parameter is clinically significant and therefore represents an AE.

#### **8.2.6 Pregnancy**

All pregnancies are to be reported from the time informed consent is signed until 90 days after the last dose of study drug.

Any female patients who become pregnant while participating in the study must be permanently discontinued from study drug. If the female partner of a male patient becomes pregnant while participating in the study, the male patient must notify the Investigator, immediately. Consent to report information regarding pregnancy outcomes should be obtained from the female partner. Any report of pregnancy for any female study participant or the partner of a male study participant must be reported within 24 hours after becoming aware of the event using the study Pregnancy Notification Form and the study’s medical monitor must be notified, immediately. The Investigator

or Investigator's designee must submit the report via fax or email to the CRO's Pharmacovigilance Department.

Every effort should be made to gather information regarding the pregnancy outcome and condition of the infant. It is the responsibility of the Investigator to obtain this information within 30 days after the initial notification and approximately 30 days post-partum. The Investigator or Investigator's designee must submit the report using the study Pregnancy Outcome Form via fax or email to the CRO's Pharmacovigilance Department within 24 hours after becoming aware.

Pregnancy complications such as spontaneous abortion/miscarriage or congenital abnormality are considered SAEs and must be reported in the clinical trial database (eCRFs) within 24 hours after becoming aware of the event and the study's medical monitor must be notified, immediately. If the eCRF is unavailable, then the Investigator must submit the report via fax or email to the CRO's Pharmacovigilance Department using the study the Serious Adverse Event Form, and also enter it into the clinical trial database when it becomes available. An elective abortion is not considered an SAE.

In addition to the above, if the Investigator determines that the pregnancy meets serious criteria, it must be reported as an SAE using the study Serious Adverse Event Form as well as the study Pregnancy Report Form. The test date of the first positive serum/urine HCG test or ultrasound result will determine the pregnancy onset date.

### 8.2.7 Abuse, Misuse, Overdose, and Medication Error

Abuse, misuse, overdose, or medication error (as defined below) must be reported to the to the CRO's Pharmacovigilance Department using the study Special Situations Report Form, whether or not the events result in an AE/SAE as described in [Section 8.2](#) and [Section 8.3](#). The 24 hour reporting requirement does not apply to reports of abuse, misuse, overdose, or medication errors unless these result in an SAE.

The categories below are not mutually exclusive; the event can meet more than one category.

- **Abuse** – Persistent or sporadic intentional intake of study drug when used for a non-medical purpose (e.g., to alter one's state of consciousness or get high) in a manner that may be detrimental to the individual and/or society.
- **Misuse** – Intentional use of study drug other than as directed or indicated at any dose (Note: this includes a situation where the study drug is not used as directed at the dose prescribed by the protocol).
- **Overdose** – Intentional or unintentional intake of a dose of a study drug exceeding the protocol-defined dose.
- **Medication Error** – An error made in prescribing, dispensing, administration, and/or use of a study drug. For studies, medication errors are reportable to the Sponsor only as defined below.

Cases of patients missing doses of product are not considered reportable as medication errors. Medication errors should be collected/reported for all products under investigation. The

administration and/or use of an expired product should be considered as a reportable medication error.

### 8.3 Serious Adverse Events

#### 8.3.1 Serious Adverse Event Definition

A Serious Adverse Event (SAE) is any untoward medical occurrence (whether considered to be related to study drug or not) that at any dose:

- Results in death
- Is life-threatening
- Note: The term ‘life-threatening’ in the definition of ‘serious’ refers to an event in which the patient was at risk of death at the time of the event; it does not refer to an event which hypothetically might have caused death if it was more severe.
- Requires inpatient hospitalization or prolongation of existing hospitalization
- Results in persistent or significant disability/incapacity
- Is a congenital abnormality/birth defect
- Is an important medical event

**Note:** Important medical events that may not result in death, be life-threatening, or require hospitalization may be considered an SAE when, based upon appropriate medical judgment, they may jeopardize the patient and may require medical or surgical intervention to prevent 1 of the outcomes listed in this definition. Examples of such medical events include allergic bronchospasm requiring intensive treatment in an emergency room or at home; blood dyscrasias or convulsions that do not result in inpatient hospitalization; or the development of drug dependency or drug abuse.

The following hospitalizations are not considered to be SAEs because there is no “AE” (i.e., there is no untoward medical occurrence) associated with the hospitalization:

- Hospitalizations for palliative therapy
- Hospitalization planned before informed consent for pre-existing conditions which have not worsened after initiation of study drug
- Hospitalization for routine maintenance of a device (e.g., pacemaker) that was in place before study entry
- Social admission (e.g., patient has no place to sleep)

However, complication(s) resulting from a hospitalization for an elective or previously scheduled surgery that meets serious criteria must be reported as SAE(s).

Adverse events that require emergency room care that do not result in hospital admission are not SAEs unless assessed by the Investigator to be an important medical event.

### **8.3.2 SAE Reporting Procedures**

All SAEs are to be reported whether or not considered causally related to THE-630. The Investigator or Investigator's designee must record all initial and follow-up SAE information in the clinical trial database (eCRFs) within 24 hours after becoming aware of the event. In the event that the clinical trial database is not available, the SAE report must be sent to the CRO's Pharmacovigilance Department within 24 hours using the study Serious Adverse Event Form, and also entered into the clinical trial database when it becomes available. The 24-hour timeframe also applies to additional new information (follow-up) on previously reported SAEs.

### **8.3.3 Information to be Provided by the Investigator for a SAE**

The Sponsor or designee will require all of the following information about the patient and the event:

- Investigator identification
- Patient identification code (e.g., sex, age, or date of birth)
- Information on study drug (e.g., start/stop date, dose, and frequency of study drug administered)
- Description of event

In addition to the above information, the Sponsor will require the Investigator's assessment of the following:

- Severity of the SAE
- Relationship of the SAE to the study drug
- Outcome of the SAE

### **8.3.4 Follow-up Information on a SAE**

The Investigator may be asked to provide additional information for any event submitted, which may include a discharge summary or extracts from the medical record. Information provided about the event must be consistent with information recorded on the electronic study case report forms (eCRF) where safety data may also be recorded (e.g., AE CRF) within 24 hours of awareness. The Investigator is responsible for management of the patients through the course of the event. There should be routine follow-up through and including a minimum of 30 days after the last administration of study drug or the Investigator/patient decision to discontinue treatment, whichever occurs later, in all patients in order to monitor for the occurrence of SAEs. If an SAE continues after the 30-day evaluation period, the patient must be followed until the event resolves, stabilizes without further involvement expected, is lost to follow-up, or dies.

### **8.3.5 Serious Adverse Event Collection Timeframe**

All SAEs (regardless of relationship to study drug) are collected from the time the patient provides informed consent through at least 30 days after the last dose of study drug. Beyond 30 days after

the last dose, all ongoing SAEs should be followed at least every 4 weeks until they resolve to baseline (or to NCI CTCAE v5.0 grade  $\leq 1$ ), stabilize, are considered by the Investigator to be chronic/irreversible, the patient is lost to follow up, or the patient dies.

### **8.3.6 Serious Adverse Event Onset and Resolution Dates**

The onset date of the SAE is defined as the date the event meets serious criteria. The resolution date is the date the event no longer meets serious criteria, the date the symptoms resolve, or the date the event is considered chronic. In the case of hospitalizations, the hospital admission and discharge dates are considered the onset and resolution dates, respectively.

In addition, any signs or symptoms experienced by the patient prior to study entry or leading up to the onset date of the SAE or following the resolution date of the SAE must be recorded as an AE, if appropriate.

### **8.3.7 Fatal Outcome**

Any SAE that results in the patient's death (i.e., the SAE was noted as the primary cause of death) must have fatal checked as an outcome with the date of death recorded as the resolution date. For all other events ongoing at time of death that did not contribute to the patient's death, the outcome should be considered not resolved, without a resolution date recorded.

For any SAE that results in the patient's death or any ongoing events at the time of death, the action taken with the study drug should be recorded as "dose not changed" or "not applicable" (if the patient never received study drug).

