##### **5.8.1 Patient Discontinuation**

Patients will be discontinued from further study drug administration in the event of any of the following:

- Intolerable toxicity as determined by the Investigator
- Progression of disease requiring an alternate therapy, in the opinion of Investigator
- Entry into another therapeutic clinical study or start of new anticancer therapy
- Significant deviation from the protocol or eligibility criteria, in the opinion of the medical monitor or Investigator
- Noncompliance with study or follow-up procedures

- Pregnancy
- Patient withdrawal of consent or decision to discontinue participation
- Termination of the study by the Sponsor
- Any other reason that, in the opinion of the Investigator, would justify removal of the patient from the study

In the event that a patient is withdrawn from the study, every effort must be made by the Investigator to document and report the reasons for withdrawal as thoroughly as possible. The reason(s) for withdrawal must be clearly reported on the appropriate page of the patient's eCRF. An eCRF must be completed for any patient enrolled, and an End-of-Treatment reason must be recorded for any patient who is enrolled, regardless of whether they receive study drug.

If a patient is discontinued from the trial for any reason, every effort must be made to perform all End-of-Treatment and 30 Days After Last Dose assessments per the schedule of events. In the event that the patient fails to return for the necessary visit(s), an effort must be made to contact the patient to determine the reason, and this information should be recorded in the appropriate source record and reported as a deviation.

All patients who permanently discontinue the study drug will be followed for survival. For patients who discontinue the study treatment due to a reason other than documented progressive disease (PD), additional tumor assessments should be documented, if available, until disease progression or start of another systemic anti-cancer therapy.

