4.1.3 Full Analysis Set

The Full Analysis Set (FAS) includes all enrolled patients who receive at least one dose of THE-630. Unless otherwise stated, all primary efficacy and safety analyses will be conducted on the Full Analysis Set.

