4.15.1 Adverse Events

A treatment-emergent adverse event (TEAE) is defined as:

- Any AE that has an onset on or after the first dose of study drug and before last dose + 30 days
- Any pre-existing AE or medical history finding that has worsened in severity on or after the first dose of study drug

A post-treatment AE is Any AE that has an onset greater than 30 days after last dose of study drug.

If an AE has missing relationship it is assumed to be related to the study drug for analysis purposes.

If a toxicity grade is missing, then the toxicity grade will be reported as missing.

The following tables will be presented for AEs:

- Overall incidence and number of TEAE, TEAEs \geq Grade 3, Treatment-Related TEAEs, Treatment-Related TEAEs \geq Grade 3, Serious Treatment Emergent Adverse Events (Treatment-Emergent SAEs), Serious Treatment-Related TEAEs (Treatment Emergent,

QMD Ref: CCI	Governing QMD: CCI
Confidentiality Statement	
CCI	

CCI		Sponsor: Theseus Pharmaceuticals, Inc.	
CCI		Protocol Number: THE630-21-101	
STATISTICAL ANALYSIS PLAN. PHASE 2-3-4			

Treatment-Related SAEs), TEAEs leading to Study Drug discontinuation, TEAEs leading to interruption of study drug, TEAEs leading to dose reduction of study drug and Fatal TEAEs.

- TEAEs by system organ class and preferred term, incidence and number of events.
- Treatment related TEAE by system organ class and preferred term, incidence and number of events.
- TEAEs \geq Grade 3 by system organ class and preferred term, incidence and number of events.
- Treatment-related TEAEs \geq Grade 3 by system organ class and preferred term, incidence and number of events.
- Serious TEAE by system organ class and preferred term, incidence and number of events.
- Serious Treatment related TEAE by system organ class and preferred term, incidence and number of events.
- TEAEs Leading to Discontinuation of Study Drug b system organ class and preferred term
- TEAEs Leading to Interruption of Study Drug by system organ class and preferred term, incidence and number of events.
- TEAEs Leading to dose reduction of Study Drug by system organ class and preferred term, incidence and number of events.
- TEAE by system organ class, preferred term and maximum toxicity, incidence.
- Treatment-Related TEAE by system organ class, preferred term and maximum toxicity, incidence.
- Fatal TEAEs by system organ class and preferred term, incidence

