14.3.1.3 DE	Adverse Events, TEAEs ≥ Grade 3 by System Organ Class and Preferred Term – Full Analysis Set <Phase>	IP	14.3.1.2
14.3.1.4 DE	Adverse Events, Treatment-Related TEAEs by System Organ Class and Preferred Term – Full Analysis Set <Phase>	IP	14.3.1.2
14.3.1.5 DE	Adverse Events, Treatment-Related TEAEs ≥ Grade 3 by System Organ Class and Preferred Term – Full Analysis Set <Phase>	IP	14.3.1.2

QMD Ref: CCI	Governing QMD: CCI
Confidentiality Statement	
CCI	

CCI		Sponsor:		Theseus Pharmaceuticals, Inc.
CCI		Protocol Number:		THE630-21-101
STATISTICAL ANALYSIS PLAN. PHASE 2-3-4				

Table Number	Table Title	Validation Method	Shell Number (if repeat)
14.3.1.6 DE	Adverse Events, Serious TEAEs by System Organ Class and Preferred Term –Full Analysis Set <Phase>	IP	14.3.1.2
14.3.1.7 DE	Adverse Events, Serious Treatment-Related TEAEs by System Organ Class and Preferred Term – Full Analysis Set <Phase>	IP	14.3.1.2
14.3.1.8 DE	Adverse Events, TEAEs Leading to Discontinuation of Study Drug by System Organ Class and Preferred Term-Full Analysis Set <Phase>	IP	14.3.1.2
14.3.1.9 DE	Adverse Events, TEAEs Leading to Interruptions of Study Drug by System Organ Class and Preferred Term-Full Analysis Set <Phase>	IP	14.3.1.2
14.3.1.10 DE	Adverse Events, TEAEs Leading to Dose Reductions of Study Drug by System Organ Class and Preferred Term-Full Analysis Set <Phase>	IP	14.3.1.2
14.3.1.11 DE	Adverse Events, TEAEs by System Organ Class, Preferred Term, and Maximum Toxicity-Full Analysis Set <Phase>	IP	
14.3.1.12 DE	Adverse Events, Treatment-related TEAEs by System Organ Class, Preferred Term, and Maximum Toxicity-Full Analysis Set <Phase>	IP	14.3.1.17
14.3.1.13 DE	Adverse Events, Fatal TEAEs by System Organ Class and Preferred Term- Full Analysis Set <Phase>	IP	14.3.1.2
14.3.1.14 DE	Adverse Events, Post-Treatment Treatment Related SAEs by System Organ Class and Preferred Term-Full Analysis Set <Phase>	IP	14.3.1.2
14.3.1.15 DE	Adverse Events, Dose Limiting Toxicities During Cycle 1 by Preferred Term and Maximum Toxicity- DLT Evaluable Analysis Set <Phase>	IP	14.3.1.2
14.3.2	Listings of Deaths, Other Serious and Significant Adverse Events		
14.3.2.1 DE	Fatal TEAEs, Listing – Full Analysis Set <Phase>	IP	
14.3.2.2 DE	All Deaths, Listing – Full Analysis Set <Phase>	IP	
14.3.2.3 DE	SAE, Listing – Full Analysis Set <Phase>	IP	

QMD Ref: CCI	Governing QMD: CCI
Confidentiality Statement	
CCI	

CCI		Sponsor: Theseus Pharmaceuticals, Inc.	
CCI		Protocol Number: THE630-21-101	

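### Protocol 8.3.7 fixes the drug-action code at 'dose not changed' for fatal SAEs and events open at death, so the SAP's tables of TEAEs leading to discontinuation, interruption or reduction may undercount if they use that code

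*Protocol*

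**What the plan says.** Protocol 8.3.7 (Fatal Outcome) sets one coding rule for every fatal SAE and for "any ongoing events at the time of death, the action taken with the study drug should be recorded as 'dose not changed". The permitted codes in full: "the action taken with the study drug should be recorded as 'dose not changed' or 'not applicable' (if the patient never received study drug". The rule does not ask whether the patient was still on drug, or whether the event had already changed dosing.

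Elsewhere the protocol expects AEs to change dosing. Section 5.6 and Table 5 provide for holds and reductions, and the reasons for stopping drug in 5.8.1 include "Intolerable toxicity as determined by the Investigator".

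SAP 4.15.1 puts these rows in the overall AE summary (Table 14.3.1.1): "TEAEs leading to Study Drug discontinuation, TEAEs leading to interruption of study drug, TEAEs leading to dose reduction of study drug and Fatal TEAEs". Tables 14.3.1.8 to 14.3.1.10 repeat discontinuation, interruption and reduction by system organ class and preferred term; Table 14.3.1.9, for example, is titled "Adverse Events, TEAEs Leading to Interruptions of Study Drug by System Organ Class and Preferred Term-Full Analysis Set". The population is treated patients only: "The Full Analysis Set (FAS) includes all enrolled patients who receive at least one dose of THE-630".

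The SAP does not say which eCRF item makes a TEAE one that led to discontinuation, interruption or reduction. The derivations in SAP 4.2 contain no such rule.

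**The concern.** The sentence probably aims to stop sites coding 'withdrawn' merely because the patient died. As written it reaches further. It also covers an event for which the drug had in fact been held, reduced or stopped while the patient was alive, and it requires a code saying that nothing was done.

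Action taken is the only AE-level link to dosing that the documents name, so it is the likely source for the four tables. If it is the source, the events lost are not a random subset: they are fatal events and toxicities that never resolved. The Phase 1 primary endpoint is the safety profile, and these tables are its direct summary of tolerability. The same report could also show a patient as having stopped drug for an AE in Table 14.1.1.4 and show no TEAE leading to discontinuation for that patient in Table 14.3.1.8.

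**Working it through.** The plan states no figure on this point, so the check is a comparison of the texts followed by simple proportions.

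**Which codes remain.** 8.3.7 allows 'dose not changed' or, for never-treated patients, 'not applicable'. The Full Analysis Set (SAP 4.1.3) holds treated patients only. For every patient in the tables, one code is left.

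**Which events can be wrongly coded.** Three conditions must hold together:

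1. The event changed dosing (Protocol 5.6, Table 5, 5.8.1).
2. The record was fatal or still open at death. This can happen well after the last dose: Protocol 8.2 follows ongoing possibly related AEs and all ongoing SAEs beyond 30 days until they resolve, stabilise or are judged chronic, and 6.4.2 follows survival until death.
3. The record had not been closed and replaced. Protocol 8.2.1 opens a new record when severity worsens, so the lower-grade record would ordinarily close and keep its own code. 8.2.1 has no matching rule for improvement. An event that caused a hold, eased and then persisted at low grade can therefore stay open on the same record.

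The clearest case is a toxicity for which THE-630 was stopped, that did not resolve, and that was still open when the patient died of GIST.

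**What else records the dose change.** Protocol 5.8 requires the reason for stopping drug on the eCRF, and SAP 4.4 tabulates it (Table 14.1.1.4). SAP 4.11 counts patients with an interruption or a reduction due to an AE (Table 14.3.5.1). Neither section is linked to the tables in 4.15.1.

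**Size per affected patient.** Inputs: 32 patients enrolled (SAP 1), assumed here all treated; planned maximum of 6 per dose level before backfill (Protocol 3.2); minimum of 3 per cohort (Protocol 3.1). For a patient with no other qualifying TEAE, the fall in incidence is 1/N:

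| Denominator | Fall per affected patient |
|---|---|
| All patients, N = 32 | 1/32 = 3.1 points |
| Dose level of 6 | 1/6 = 16.7 points |
| Dose level of 3 | 1/3 = 33.3 points |

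The number affected is not in the documents. For an assumed 1 to 5 such patients, the overall undercount runs from 1/32 = 3.1 to 5/32 = 15.6 points. A patient with another qualifying TEAE still counts in the overall incidence. Where a table also reports the number of events, that count falls by one for each miscoded event regardless.

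**Direction.** The rule can turn a true 'stopped', 'interrupted' or 'reduced' into 'dose not changed', never the reverse. The error can only be an undercount.

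**The case against.** The strongest reply is that the loss is not demonstrated. No section says that these tables are built from the action-taken field, and the AE eCRF completion guidelines are a separate document (Protocol 7.3.9). That stands, and the point is conditional for this reason. A reader might infer that the affected events certainly drop out of the tables; the documents do not support that.

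A second reply concerns the fatal case. A reader might picture a Grade 4 toxicity that stops the drug and then kills the patient, with the discontinuation erased. Under 8.2.1 the worsening to Grade 5 should open a new record, so the Grade 4 record may close with its own code. The Grade 5 record begins after the drug was stopped, and 'dose not changed' is not false for it. This largely stands, and it moves the weight of the point to events unresolved at death.

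Third, the pool is narrow. Follow-up ends when an event resolves, stabilises or becomes chronic, and for SAEs a judgement of chronic supplies a resolution date (8.3.6). This also stands, although open records at death remain possible.

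Fourth, the severe events stay visible: the fatal, serious, Grade 3 or higher and maximum-toxicity displays do not depend on the action code, and DLTs carry their own database flag (SAP 4.2.13.2). The disposition and exposure tables may keep the information at patient level. This limits the harm, but it does not make the four tables correct, and it creates the possible contradiction within one report.

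Finally, a reader might infer that the choice of RP2D was biased. Escalation was decided at safety review meetings (Protocol 5.3), RP2D was to rest on an integrated evaluation (5.5), and enrolment stopped with Phase 2 not to be started (SAP 1). That inference is not supported.

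**Conclusion.** The inconsistency is real and conditional in its effect. Followed as written, 8.3.7 makes sites record an untrue action for a treated patient's event that changed dosing and was later still open at death, and nothing in the SAP corrects this. Whether Tables 14.3.1.1 and 14.3.1.8 to 14.3.1.10 are affected depends on their using the action-taken field, which is likely but not stated.

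The effect per affected patient with no other qualifying TEAE is 3.1 points overall, assuming all 32 were treated, and 16.7 points in a six-patient dose level, which is an illustration. The total is unknown. Events in survivors and records closed before death are untouched. This is a data-recording and derivation problem in the tolerability tables, and it is cheap enough to be worth correcting.

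**What to change.** 1. **Protocol 8.3.7 or the eCRF completion guideline.** Limit 'dose not changed' to events for which no action was taken with study drug before death. Otherwise record the action actually taken because of the event. Keep 'not applicable' for never-treated patients.
2. **SAP 4.15.1.** Define TEAEs leading to discontinuation, interruption or reduction by reconciling the AE action code with the dosing records and the End-of-Treatment reason, and name the source fields. Check the result against Tables 14.1.1.4 and 14.3.5.1.
3. **Data.** Before lock, query the existing fatal and ongoing-at-death records for the action taken.

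With enrolment closed, items 2 and 3 do most of the work; item 1 covers records still to be entered. The cost is one clause, one derivation line and a small query burden, and the reported rates may rise slightly. Nothing here changes how patients are treated.
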